4.1.3 V1 visit

The V1 visit will occur 2 weeks after V0 (\pm 3 days). The following assessments will be conducted at V1:

- Physical examination and vital signs assessment, according to [Sections 4.2.1.2](#) and [4.2.1.5](#),
- Weight and calculation of BMI,
- Blood and urine sample collection for haematology, blood chemistry, urinary analysis according to [Section 4.2.1.8](#),
- Query for changes in concomitant medications,
- Recording of AEs (if any),
- Appointment for the next visit,
- eCRF recording of data collected.

4.1.4 V2 visit

The V2 visit will occur 4 weeks after V0 (\pm 4 days).

The day before V2 the patient will go on site to be administered the IMP at 20:00. The day of V2 the patient must be present on site around 7:30 as a blood sample for PK will be collected in the morning of V2 before the IMP administration that will take place at 08:00. Patients can, but are not forced to, spend the night at the site between these 2 drug administrations, upon agreement between both parties. Patients who leave far away from the investigational site and cannot be hospitalized during the night before V2 for logistical reasons are allowed to take the evening study treatment at home on the day before V2. In this case, the time of dosing must be set by the study team, depending on the time of planned first PK blood sampling at V2, allowing a 12-hour interval between last drug intake and blood sampling. If the patient cannot take the drug at the exact time requested by the hospital, he must note the actual time of drug intake. Patients who do not spend the night in the hospital must be provided with a sterile container to collect morning urine. It will be given to the patient at V1 for those who will not come to the hospital for drug administration on the day before V2.

The following assessments will be conducted at V2:

- Physical examination and vital signs assessment, according to [Sections 4.2.1.2](#) and [4.2.1.5](#),
- Weight and calculation of BMI,
- 12-lead ECG ([Section 4.2.1.6](#)),
- Blood and urine sample collection for haematology, blood chemistry, urinary analysis according to [Section 4.2.1.8](#),
- Crystalluria analyses according to [Section 4.2.1.9](#),
- PK blood samples collection according to [Section 4.2.2.2](#),

- Query for changes in concomitant medications,
- Recording of AEs (if any),
- Pregnancy test in WOCBP. In addition to tests performed at hospital visits, pregnancy tests will be performed at monthly intervals during treatment and until the end of relevant systemic exposure. If a positive result is detected with urine pregnancy test, a serum pregnancy test will be performed to confirm the results.
- Dispensation of study product to the patient,
- Appointment for the next visit,
- Patients will be given a prescription for blood sampling (creatininemia and eGFR) to be performed at V2 + 1 month in a local laboratory. Results of these analyses will be sent to the site in real time,
- eCRF recording of data collected.

4.1.5 V3 visit

The V3 visit will occur 9 weeks after the V2 (\pm 4 days).

The following assessments will be conducted:

- Physical examination and vital signs assessment, according to [Sections 4.2.1.2](#) and [4.2.1.5](#),
- Weight and calculation of BMI,
- 12-lead ECG ([Section 4.2.1.6](#)),
- Blood and urine sample collection for haematology, blood chemistry, and urinary analysis according to [Section 4.2.1.8](#),
- Query for changes in concomitant medications,
- Recording of AEs (if any),
- ALSFRS-R measurement,
- ALS-MITOS measurement,
- King's College score measurement,
- Bioelectrical Impedance Analysis
- C-SSRS evaluation,
- SVC assessment,
- Sniff test⁷,
- ABG,
- Collection of blood samples for biomarkers analysis according to [Section 4.2.2.3](#),

⁷ The sniff test is optional. It will be performed only in sites that have the equipment and resources to perform this test.

- Pregnancy test in WOCBP. In addition to tests performed at hospital visits, pregnancy tests will be performed at monthly intervals during treatment and until the end of relevant systemic exposure. If a positive result is detected with urine pregnancy test, a serum pregnancy test will be performed to confirm the results.
- Dispensation of study product to the patient,
- Appointment for the next visit,
- Patients will be given a prescription for blood sampling (creatininemia and eGFR) to be performed at V3 + 1 month and V3 + 2 months in a local laboratory. Results of these analyses will be sent to the site in real time,
- eCRF recording of data collected.

4.1.6 V3bis visit

The V3bis visit will occur 6.5 weeks after the V3 visit (\pm 4 days).

The following assessments will be conducted:

- Physical examination: cardiac auscultation, heart rate, systolic and diastolic blood pressure),
- 12-lead ECG,
- Blood sample collection for measurement of electrolytes (Na, K, Ca, Cl, Mg, Ph, HCO3), BNP, troponin, D-Dimers, INR, and prothrombin time.

For patients who have already completed the V3 visit and are very close (\leq 2 weeks) to the V4 visit when the decision is made to add the V3bis visit, a phone call should be made to investigate the patient's condition. If any sign or symptom is mentioned, the patient should come to the hospital as soon as possible for further investigations, otherwise the V3bis visit will not be performed and the patient will undergo the V4 visit as planned.

For patients who have completed the V3 visit and have the V4 visit expected in more than 2 weeks but less than 6.5 weeks when the decision is made to add the V3bis, the V3bis visit should be made as early as possible, depending on the site's and patient's possibilities. If an onsite visit is impossible, a phone call must be made to investigate the patient's condition.

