Study design:	
Prospective, international, randomised, double-blind, placebo controlled, multicentre, parallel group study.
 
Patients will be randomised in a 2:1 allocation ratio to receive either IFB-088 + riluzole 100 mg or placebo + riluzole 100 mg.
 
Patients will be treated over a 6-month period. After a screening/consent visit, patients will undergo clinic visits at randomisation (V0), at 2 weeks (V1), and at months 1 (V2), 3 (V3), 4.5 (V3bis) and 6 (V4). In addition to these hospital visits, patient will undergo urine analysis (dipstick) and blood sampling for measurement of creatinine one week after V0, as well as blood sampling for measurement of creatinine and calculation of eGFR at months 2, 4 and 5. At the V2 visit, in addition to other assessments, patients will undergo blood sampling for PK measurements and urine sampling for crystalluria examination. Laboratory parameters, as well as physical examination and vital signs assessment to assess safety will be performed at each visit for safety purpose and crystalluria examination will be repeated at the follow-up visit, performed one month \pm one week after V4, or in case of premature discontinuation.
 
Safety will be monitored over the course of the study by a data and safety monitoring board (DSMB).
 
If needed, compliance with coronavirus disease 2019 (COVID-19)-related rules will be followed and adjustments might be necessary accordingly.
 
Unless they already obtained treatment research initiative to cure ALS (TRICALS) certificates, study examiners will undergo online training to ensure uniformity of study procedures across sites, and inter-rater variability will be documented. For investigators who cannot undergo the TRICALS training, certification from the Barrow Neurological Institute is acceptable.
 
Management of frail functions will be standardised as much as possible.
												
Planned number of patients:	The minimum required sample size for this study has been estimated at 42 evaluable patients, 28 receiving IFB-088 and 14 receiving placebo. Assuming a 15% drop-out rate, 50 patients will be randomised.												

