^{††} A **prescription** will be given to patients at V2 to perform blood sampling for creatininemia and eGFR in a local laboratory at V2 + 1 month (i.e., V0 + 2 months).

^{†††} A **prescription** will be given to patients at V3 to perform blood sampling for creatininemia and eGFR in a local laboratory at V3 + 1 month and V3 + 2 months (i.e., V0 + 4 months and 5 months respectively).

^{ff} Prior to CSF sampling, only in case CSF sampling is planned.

^{fff} Only in patients who accepted to undergo lumbar puncture and do not have contraindications (see section 4.2.2.3).

a: first intake of IMP on site at baseline V0 visit (see section 4.1.2).

x: cardiac auscultation, heart rate, systolic and diastolic blood pressure.

y: selected blood markers, detailed in section 4.1.6.

z: independent of CSF sampling.

(1) Patient will have to sign informed consent form for the study before any study procedure.

(2) Sniff test is optional. It will be performed only in sites that have the equipment and resources to perform this test.

(3) The day before V2 the patient will go on site to be administered the IMP at 20:00.

(4) C-SSRS “Lifetime” version at screening visit. C-SSRS “Since Last Visit” version at V3, V4 and premature discontinuation visits.

BMI: body mass index, ECG: electrocardiogram, AEs: adverse events, ALSFRS-R: revised ALS functional rating scale, ALS-MITOS: ALS Milano-Torino staging,

ALSAQ-40: ALS assessment questionnaire, SVC: slow vital capacity, ABG: arterial blood gases, PK: pharmacokinetics, CSF: cerebrospinal fluid, V: visit, FU: follow-up, miU/ml: milli-international units per millilitre.

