This will include temperature, systolic and diastolic arterial pressure and heart rate. Information about the vital signs must be present in the source documentation at the study site. Blood pressure and heart rate will be measured after the patient has rested for 5 minutes, in both supine position and standing.

4.2.1.6 *Electrocardiogram*

A standard 12-lead ECG will be performed in triplicates in a resting position. Prior to the recording the patient should be at rest for at least 5 minutes. The ECG printout will be reviewed by the investigator.

4.2.1.7 *Laboratory assessments*

Accredited local and central laboratories will be used for analysis of specimens collected at each visit, according to [Table 3](#). Analyses will include:

- Complete laboratory evaluations (hematology, biochemistry, electrolytes, liver function, renal function, urinalysis) for safety assessment,
- Biomarker assessment ([Section 4.2.2.3](#)),
- Pregnancy test,
- Crystalluria ([Section 4.2.1.9](#)),
- PK.

Laboratory values that exceed the thresholds of normal laboratory values must be commented by the investigator on source documents and respective patient's laboratory eCRF page.

For each visit, the drawn amount of blood, urine and CSF required is detailed in [Table 3](#).

Table 3 – Schedule and location of the blood, urinary and cerebrospinal fluid tests

Sample	Assessment	Screening	Baseline (V0)	V1	V2	V3	V3bis	V4	V-FU	Premature discontinuation	Bio bank	Quantity per visit	Laboratory
Whole blood (EDTA/lithium heparin tube)	Safety (haematology)	X	X*	X	X	X		X	X	X			Local
Serum (serum-separating tube)	Safety (electrolytes, biochemistry, liver function, renal function)	X	X* ^a	X	X ^{a a}	X ^{a a} ^a	X	X	X	X		20 ml	
Plasma (EDTA tube)	Biomarkers		X			X		X		X	X	20 ml	Central
Whole blood (PAXgene blood RNA tube)	Biomarkers		X					X		X	X	5 ml	Central
Plasma (lithium heparin tube)	PK				X							10 ml	Central
Plasma (lithium heparin tube)	Efficacy (arterial blood gases)	X				X		X		X		2 ml	Local
Urine	Safety	X	X* [†]	X	X	X		X	X	X		50 ml	Local
Urine	Crystalluria				X				X	X		50 ml	Central
Urine	Biomarkers		X					X		X	X	100 ml	Central
Blood/urine	Pregnancy test	X**	X***		X***	X***		X***	X**	X***		2 ml/1 ml	Local
CSF	Biomarkers	X						X		X	X	1.8 ml	Central

CSF: cerebrospinal fluid, EDTA: ethylenediaminetetraacetic acid, V: visit, FU: follow-up.

* If needed, based on investigator's judgement.

† Additional urine analysis (dipstick) at V0 + one week.

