^a Additional blood sampling for creatinine measurement at V0 + one week.^{a a} Additional blood sampling for creatinine measurement and calculation of eGFR at V2 + 1 month.^{a a a} Additional blood sampling for creatinine measurement and calculation of eGFR at V3 + 1 month and V3 + 2 months.

** Blood pregnancy test at screening and FU visit (V-FU).

*** Urine pregnancy test on a monthly basis until end of exposure to study treatment.

4.2.1.8 *Blood and urine safety analysis*

Blood and urine safety analyses will be performed at each visit after screening, except at baseline (V0) unless required by occurrence of intercurrent event since screening. Blood will be drawn via a hypodermic needle inserted into a vein in the arm and collected in the appropriate tube(s), according to [Table 3](#). The patient must be fasting overnight from 22:00. Urine specimens will be obtained by providing participants with a collection cup and instructions for the collection.

Further details on blood and urine sample processing, storage and shipping procedures will be provided in the laboratory procedures manual (LPM) provided by the sponsor.

The following parameters will be assessed for safety assessment:

Haematology

Haematology will include count of red blood cells, haemoglobin, haematocrit, total white blood cells count, platelet count, and a differential count including neutrophils, lymphocytes, monocytes, eosinophils, basophils.

Biochemistry

Biochemistry will include glucose, total cholesterol, high-density lipoprotein (HDL) cholesterol and calculated low-density lipoprotein (LDL) cholesterol, triglycerides, C-reactive protein, troponin T, creatine kinase, and uric acid.

Electrolytes

Electrolytes will include sodium, potassium, chloride, bicarbonate, calcium, magnesium, phosphorus.

Renal function

Renal function panel will include creatinine, blood urea nitrogen, estimated glomerular filtration rate, total protein.

Liver function

Liver function panel will include total protein, albumin, total bilirubin, direct bilirubin, alkaline phosphatase (ALP), aspartate aminotransferase (AST), alanine aminotransferase (ALT), gamma-glutamyl transferase (GGT), lactate dehydrogenase (LDH).

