According to section 4.4 of riluzole SmPC, ALT should be measured every month during the first 3 months of treatment, every 3 months during the remainder of the first year, and periodically thereafter. This monitoring should be performed more frequently in patients with ALT increase under treatment. Depending on the date when riluzole has been initiated and the kinetics of ALT, additional measurements of ALT might therefore be necessary.

Urinary analysis

It includes blood, leukocytes, pH, glucose, and proteinuria assessed by means of commercial urine dipsticks. In case of proteinuria ≥ 30 mg/dL on the dipstick, 24-hour protein is also performed.

Urinary analysis will also include measurement of beta 2 microglobuline or albumin-to-creatinine ratio in mg/g or mg/mmol, microalbumine, creatinine, and proteins, and cytobacteriological examination of urine (CBEU). All these analyses will be performed in a spot urine sample.

4.2.1.9 *Crystalluria*

Microscopic analysis of urine will be performed to investigate drug-related crystalluria. Sample of first-morning micturition will be collected at the V2 visit. The sample will be collected by the hospital staff if the patient has been hospitalised the day before (see [Section 4.1.4](#)), or by the patients themselves if they have spent the night outside the hospital. In this case, patients will receive a sterile dedicated container either on the day before the V2 visit when they go on site for the IMP administration for PK assessment, or at the end of the V1 visit for those who will take the evening treatment at home before V2. A sample of 50 ml will be frozen at -20°C and sent to a central laboratory that will perform microscopic analysis within 7 days after urine collection. Urine freezing should be done within 3h of collection.

Crystalluria will also be investigated at the V-FU visit or at the premature discontinuation visit if any. Urine will be collected when the patient arrives in the hospital for his visit.

4.2.1.10 *Pregnancy testing*

All female patients of childbearing potential will have to perform a blood beta-human chorionic gonadotropin (beta-HCG) testing at screening. For WOCBP, high sensitivity urine pregnancy test will be performed at baseline and repeated on a monthly basis during treatment and until the end of relevant systemic exposure, as well as in case of premature discontinuation and at any time if pregnancy is suspected (sensitivity 25 mIU/ml or more).

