5.3 WITHDRAWAL OF THE PATIENT

Patients may withdraw from the study at any time without having to provide justification and without penalty to their continuing medical care.

The investigators may withdraw patients from the study for the following reasons:

- Patient withdrawing the consent,
- If, in the investigator's opinion, continuation in the study would be detrimental to the patient's well-being, in particular in case of an AE,
- If, in the investigator's opinion, the patient is unable to maintain the schedule or is non-compliant,

¹¹ Decline will be calculated as follows: 48 minus ALSFRS-R score at the time of inclusion divided by number of months since occurrence of first symptoms of disease, as reported by the patient.

- If the patient becomes pregnant during the study,
- If the patient meets one of the following criteria for permanent drug discontinuation:
 - Increased ALT or AST levels $\geq 5 \times$ ULN.
 - ALT or AST > 3 ULN and total bilirubin levels > 2 ULN.
 - Neutropenia.
 - Symptoms evocative of interstitial lung disease: dry cough and/or dyspnoea, bilateral diffuse lung opacities.
- Lost to FU. A participant will be considered lost to FU if he/she repeatedly fails to return for scheduled visits and is unable to be contacted by the study site. Site personnel are expected to make diligent attempts to contact participants who fail to return for a scheduled visit or are otherwise unable to be followed up by the site.

The date of withdrawal and the principal reason for withdrawal must be recorded in the eCRF and in the patient's records. No additional data will be collected for withdrawn patients. Every effort must be made to contact patients who did not come back for a planned visit/contact.

Every effort will be made to ensure that patients who do not complete all study visits return to the site for the premature discontinuation visit ([Section 4.1.9](#)), as soon as possible and no later than 4 weeks after the last IMP intake. Patients who withdraw due to an AE or SAE will be given appropriate care under medical supervision until the symptoms resolve or the patient's condition becomes stable.

Patients who prematurely withdrew from the study or are lost to FU will not be replaced by new patients.

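### Between V3 (week 13) and the end of dosing at V4 (week 26), the visit lists schedule no ALT/AST, bilirubin or neutrophil test that could trigger a section 5.3 stop of IFB-088

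*Protocol*

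**What the plan says.** Protocol section 5.3 lists four laboratory or symptom criteria for permanent drug discontinuation: ALT or AST at least 5 times ULN; "ALT or AST > 3 ULN and total bilirubin levels > 2 ULN"; neutropenia; and symptoms suggesting interstitial lung disease. The first three need a blood test.

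The visit lists in sections 4.1.3 to 4.1.5 and 4.1.7 call for haematology and blood chemistry at V1, V2, V3 and V4. The extra local draws at months 2, 4 and 5 are for creatinine and eGFR (section 3.1).

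For V3bis, the texts differ:

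- Section 4.1.6 specifies "Blood sample collection for measurement of electrolytes (Na, K, Ca, Cl, Mg, Ph, HCO3), BNP, troponin, D-Dimers, INR, and prothrombin time". It names no liver enzyme, bilirubin or blood count.
- Table 2 note y points to that list: "y: selected blood markers, detailed in section 4.1.6".
- Table 3 ticks V3bis, without a footnote, on the row "Safety (electrolytes, biochemistry, liver function, renal function"). It leaves the haematology cell blank.
- Section 4.2.1.8 is general: "Blood and urine safety analyses will be performed at each visit after screening, except at baseline (V0"). It makes no exception for V3bis.
- The synopsis is general too: "Laboratory parameters, as well as physical examination and vital signs assessment to assess safety will be performed at each visit for safety purpose".

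Dosing lasts 26 weeks (section 3.4), and SAP section 5.2.10 takes V4 as the date of last intake for completers.

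**The concern.** A stopping criterion protects a patient only if something measures it while dosing can still be stopped. If section 4.1.6 is followed, a transaminase rise or neutrophil fall that begins silently after a normal V3 is first seen by a scheduled test at V4, when the last dose is due anyway.

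Two facts make this worth attention. Earlier repeated human dosing of IFB-088 was 14 days in healthy volunteers (section 1.1.2.2), and every patient also takes riluzole, which section 1.3 says can cause liver toxicity. The test frequency also sits oddly against the criteria: creatinine is measured at months 2, 4 and 5 although section 5.3 has no renal criterion, while the analytes with stopping thresholds are measured less often.

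There is a reporting consequence too. An abnormality first found at V4 would be recorded as an adverse event if clinically significant (section 4.2.1.1), but it could hardly count towards the primary endpoint on events that lead to interrupted or stopped dosing. That endpoint therefore depends partly on when the tests are done.

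**Working it through.** **Schedule.** V2 is at week 4. V3 = 4 + 9 = 13. V3bis = 13 + 6.5 = 19.5. V4 = 19.5 + 6.5 = 26. These reproduce Table 2.

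**Gaps between scheduled liver and neutrophil tests.** On treatment they fall at weeks 2, 4, 13 and 26, so the gaps from V0 are 2, 2, 9 and 13 weeks. The last is 91 days, or 83 to 99 days with the 4-day window of Table 2 applied at both ends. Between week 4 and V4, (9 + 13)/26 = 85% of planned dosing has one intermediate test.

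**Which V3bis text governs.** Table 2 note y defers to section 4.1.6. The Table 3 tick is on a composite row, and V3bis does draw electrolytes and troponin (a biochemistry item in section 4.2.1.8), so the tick can be true without liver tests. The blank haematology cell agrees with section 4.1.6. For neutrophils, only the two general sentences point the other way. The most specific reading is that V3bis omits these tests. The SAP adds little: section 5.12.3.2 leaves V3bis out of its visit list for classifying these parameters, but it does so for electrolytes as well, which are drawn there.

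**Delay model.** Assume onset is silent, persists, and is uniform over the 13 weeks from V3 to V4. If the tests split this span into gaps g, then:

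- mean delay = sum of g² / (2 × 13);
- share detectable before V4 = (13 − last gap)/13.

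One month is 365.25/12/7 = 4.348 weeks.

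| Tests added | Gaps (weeks) | Mean delay (weeks) | Detectable before V4 |
|---|---|---|---|
| None | 13 | 169/26 = 6.5 | 0% |
| V3bis | 6.5, 6.5 | 84.5/26 = 3.25 | 6.5/13 = 50% |
| V3 + 1 and V3 + 2 months | 4.348, 4.348, 4.304 | 56.33/26 = 2.17 | 8.696/13 = 66.9% |
| All three | 4.348, 2.152, 2.196, 4.304 | 46.88/26 = 1.80 | 66.9% |

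**Sensitivity of the V3bis row.**

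- Moving V3bis by 4 days either way (5.93 or 7.07 weeks after V3) gives a mean delay of 3.28 weeks and a share of 45.6% or 54.4%.
- If a proportion p attend in person, delay = 6.5 − 3.25p and share = 50% × p. For p = 0.75: 4.06 weeks and 37.5%. For p = 0.5: 4.88 weeks and 25%.
- For onset in weeks 13 to 19.5, mean dosing after onset falls from 13 − 3.25 = 9.75 weeks to 3.25 weeks. The 6.5 weeks avoided are 6.5/26 = 25% of planned dosing, or 5.5 weeks if results take 7 days.

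The attendance term matters because, for patients already past V3 and 2 to 6.5 weeks from V4 when the visit was introduced, section 4.1.6 says: "If an onsite visit is impossible, a phone call must be made". Patients within 2 weeks of V4 have a call and, if they report no symptoms, no V3bis visit.

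**The case against.** The strongest reply is that monitoring follows the known risk. As the protocol summarises it, the animal programme (up to 26 and 39 weeks) points to the kidney and reports no liver or neutrophil signal, and renal function is tested often. The hepatotoxicity the protocol names is riluzole's. Patients enter after at least one month of stable, well-tolerated riluzole, so the monthly ALT phase quoted in section 4.2.1.8 is over by V3, and the later cadence, "every 3 months during the remainder of the first year, and periodically thereafter", is met by V3 and V4. V3bis is a cardiac and coagulation visit by content. All of this stands, and there is no breach of the riluzole monitoring rule. But that rule covers ALT only. Its closer testing depends on an ALT rise having been seen, and it does not address neutrophils or IFB-088.

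Three stronger readings are tempting, and the documents do not support them:

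- A reader might infer that the protocol leaves the content of V3bis wholly unresolved. Note y resolves most of it. What remains is a missing footnote in Table 3 and a missing exception in two general sentences.
- A reader might infer that a result first seen at V4 cannot be acted on. That holds only for stopping IFB-088. The result can still inform riluzole management, the follow-up visit repeats haematology and chemistry about four weeks later, and symptom-driven tests and DSMB review remain.
- A reader might take 0% against 67% as cases missed. It is the geometry of test spacing under an assumed onset pattern. If sites followed Table 3 literally and ran liver tests at V3bis, adding them there would gain nothing.

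**Conclusion.** The point holds as an inexpensive safety improvement with a documentation repair. On the most specific text, three of the four section 5.3 criteria have no scheduled test that could lead to stopping IFB-088 in the last 13 of 26 weeks. Under silent, persistent, uniform onset, the existing local draws would take the share detectable before V4 from 0% to about 67% and mean delay from 6.5 to about 2.2 weeks. V3bis alone would give 50% and 3.25 weeks with full in-person attendance. Conditional ALT tests under the riluzole rule and symptom-driven tests are not counted. The case rests on the protocol's own criteria and the short human exposure, not on evidence that such events are expected.

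**What to change.** 1. Add ALT, AST, total bilirubin and neutrophil count to the local draws at V3 + 1 month and V3 + 2 months (sections 3.1 and 4.1.5, notes to Tables 2 and 3). This is the better place: results already reach the site in real time, and the draws do not depend on V3bis attendance. Adding the same tests at V3bis is an alternative or a supplement. On top of the local draws it does not raise the share detectable before V4, but it shortens mean delay from 2.17 to 1.80 weeks.
2. Footnote the Table 3 serum tick at V3bis with the analytes actually run. Tick haematology there only if a blood count is added.
3. In section 4.2.1.8 and the synopsis sentence, state that V3bis tests are those listed in section 4.1.6.

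Steps 2 and 3 are needed even if no test is added. The section 5.3 criteria stay as they are. The SAP already lists V3bis values and summarises clinically significant laboratory abnormalities across the whole study. If the local draws are used, the note in SAP section 5.12.3.2 that names only creatinine and GFR for those time points should be extended by a line.

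The cost is a protocol amendment, one extra tube, a few routine assays, and more abnormal values to review, with no new visit. The benefit reaches only patients still on treatment when the amendment takes effect. The synopsis planned last patient out for the third quarter of 2024 and the SAP is dated November 2024; actual dates are not given. If dosing has finished, the useful action is to document which tests were run at V3bis and carry the corrected schedule into any successor protocol.
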